6.2.2 Measurements recorded in eDiary (new patients only)

Patients will be supplied with a handheld eDiary for pilot training and the OIC confirmation period. At Visit S1, new patients will be carefully instructed and trained on how to fill in the eDiary and how to handle the device. Written information will be supplied to each patient. The patients must understand and be willing to use the eDiary and be instructed on how and where to request help if problems occur. If a patient does not fill out the eDiary, there will be a prompt at the end of the day informing the patient that no data has been recorded and to confirm that they have not had any BMs that day. Additional reminder prompts for data consistency will also be included (eg, if a patient records 2 BMs, but fills out the symptom data only once, they will be prompted at the end of the day to fill out the symptom data for the other BM).

The eDiary will be completed each day from the evening of Visit S1 to the morning of Visit R1 (randomization), including days of study visits. The eDiary will include the following daily recordings:

- Date and time of BM (recorded at the time of each BM)
- Stool consistency (BSS) (recorded at the time of each BM)
- Straining (recorded at the time of each BM)
- Complete/incomplete evacuation (recorded at the time of each BM)
- Pain level (NRS) recorded each evening for the average and worst pain level that occurred during the previous 24 hours
- Date and time of use of laxative rescue medication (bisacodyl or enema) recorded at the time the medication is taken
- Date and time of use of opioid medication for breakthrough pain recorded at the time the medication is taken, as well as the medication and dose administered (note: maintenance opioid regimen would be reported separately on the opioid dose eCRF).

6.2.2.1 Bowel movements

All BMs will be recorded as they occur.

6.2.2.2 Stool consistency (Bristol Stool Scale)

Patients will rate stool consistency through completion of the BSS after each BM.

The BSS is a medical aid designed to classify the form of human feces into 7 categories. It was developed by Heaton at the University of Bristol and was first published in the Scandinavian Journal of Gastroenterology in 1997 (Lewis and Heaton 1997).

The form of the stool depends on the time it spends in the colon. The 7 stool types are:

1. Separate hard lumps, like nuts (hard to pass)
2. Sausage-shaped, but lumpy
3. Like sausage, but with cracks on its surface
4. Like a sausage or snake, smooth and soft
5. Soft blobs with clear cut edges (passed easily)
6. Fluffy pieces with ragged edges, a mushy stool
7. Watery, no solid pieces.

Types 1 and 2 indicate constipation, Types 3 and 4 represent “ideal stools,” and Types 5 to 7 are tending towards diarrhea or urgency.

6.2.2.3 Straining

The degree of straining with each BM will be recorded at the time of the BM and after the BSS. A single-item straining question, developed and validated through 1:1 interviews with OIC patients will be asked via the electronic diary. The question is provided below:

“How much did you strain during your bowel movement?”

1=Not at all

2=A little bit

3=A moderate amount

4=A great deal

5=An extreme amount.

6.2.2.4 Complete/incomplete evacuation

Patients will record the completeness of evacuation at the time of each BM and after the straining question. A single question on the completeness of evacuation, developed and validated through 1:1 interviews with OIC patients will be asked via the electronic diary. The question is provided below:

“Did you feel like your bowels were completely empty after the bowel movement?”

Patients will provide a yes or a no response to the complete/incomplete evacuation question.

6.2.2.5 Pain level

Patients will rate their pain level at the end of each day, using the NRS (see Section 6.3.7).

6.2.2.6 Use of laxative rescue medication

All bisacodyl and enema laxative rescue medication will be recorded at the time the medication is taken.

6.2.2.7 Use of opioid medication for breakthrough pain

Opioid medication for breakthrough pain will be recorded in the eDiary at the time the medication is taken.

6.2.3 Additional procedures including follow-up procedures

Additional procedures (and follow-up procedures) during the visits after screening are referenced in the Study Plan (Table 1).

6.3 Safety

The PI is responsible for ensuring that all staff involved in the study is familiar with the content of this section.

6.3.1 Safety variables

Safety variables include:

- Incidence, nature, and intensity of AEs, treatment-related AEs, SAEs, AEs leading to discontinuation, and specific safety areas of interest
- Mean daily opioid dose for Months 1, 3, 6, 9, and 12
- Mean bisacodyl dose per week for Months 1, 3, 6, 9, and 12 (NKTR-118 group only)
- Change from baseline in NRS pain score for Week 1, Week 2, Months 1, 2, 3, 6, 9, and 12.
- Observed values and change from baseline in composite score in modified Himmelsbach scale for the evaluation of centrally mediated opioid withdrawal symptoms for Week 1, Months 1, 3, 6, 9, and 12
- Changes in vital signs and physical examination
- Changes in laboratory assessments (ie, chemistry, hematology, and U/A)
- Changes in ECGs

6.3.2 Definition of adverse events

An AE is the development of an undesirable medical condition or the deterioration/exacerbation of a pre-existing medical condition following or during exposure to a pharmaceutical product, whether or not considered causally related to the product. An undesirable medical condition can be symptoms (eg, nausea, chest pain), signs (eg, tachycardia, enlarged liver), or the abnormal results of an investigation (eg, laboratory findings, ECG). In clinical studies, an AE can include an undesirable medical condition occurring at any time, including run-in or washout periods, even if no study treatment has been administered.

The term AE is used to include both serious and non-serious AEs.

6.3.3 Definitions of serious adverse event

An SAE is an AE occurring during any study phase (ie, run-in, treatment, washout, follow-up), that fulfills 1 or more of the following criteria:

- Results in death
- Is immediately life-threatening
- Requires in-patient hospitalization or prolongation of existing hospitalization
- Results in persistent or significant disability/incapacity or substantial disruption of the ability to conduct normal life functions
- Is a congenital abnormality or birth defect
- Is an important medical event that may jeopardize the patient or may require medical intervention to prevent 1 of the outcomes listed above.

For further guidance on the definition of an SAE, see [Appendix B](#) to the CSP.

6.3.4 Recording of adverse events

Time period for collection of adverse events

All AEs will be collected from the time of signature of informed consent to the follow-up visit (Visit R15), whether or not related to the IP and must be recorded on the eCRF. Unsolicited reports of SAEs will also be collected for 30 days after the last dose of study drug.

Follow-up of unresolved adverse events

Any AEs that are unresolved at the patient's last AE assessment in the study are followed up by the investigator for as long as medically indicated, but without further recording in the eCRF. AstraZeneca or its representative retains the right to request additional information for any patient with ongoing AE(s)/SAE(s) at the end of the study, if judged necessary.

Variables

The following variables will be collect for each AE;

- AE (verbatim)
- The date when the AE started and stopped
- Maximum intensity or intensity or changes in intensity
- Whether the AE is serious or not
- Investigator causality rating against the study drug (yes or no)
- Action taken with regard to IP
- AE caused patient's discontinuation from study (yes or no)
- Outcome.

In addition, the following variables will be collected for SAEs:

- Date AE met criteria for SAE
- Date investigator became aware of SAE
- Seriousness criteria
- Date of hospitalization
- Date of discharge
- Probable cause of death
- Date of death
- Autopsy performed
- Causality assessment in relation to study procedure(s)
- Causality assessment in relation to other medication
- Description of AE (including treatment administered and dechallenge/rechallenge information, if applicable).

Intensity is defined as follows:

- Mild (awareness of sign or symptom, but easily tolerated)

- Moderate (discomfort sufficient to cause interference with normal activities)
- Severe (incapacitating, with inability to perform normal activities).

Other reporting guidance

It is important to distinguish between serious and severe AEs. Severity is a measure of intensity whereas seriousness is defined by the criteria in Section 6.3.3. An AE of severe intensity need not necessarily be considered serious. For example, nausea that persists for several hours may be considered severe nausea, but not an SAE. On the other hand, a stroke that results in only a limited degree of disability may be considered a mild stroke, but would be an SAE.

If a diagnosis of the patient's condition has been made, then the diagnosis should be recorded as the SAE or the AE. In instances of well-recognized symptoms, they can be recorded as the commonly used diagnosis (eg, fever, runny nose, and cough can be recorded as "flu"). However, if a diagnosis of the patient's condition has not been made, or if the individual symptoms are not well recognized, then the individual symptoms should be recorded separately.

Should an overdose occur, it must be reported in accordance with the procedures described in Section 13.2. All overdoses, with or without associated symptoms, should be reported as AEs.

Suicide and attempted suicide, irrespective of the method, but occurring in connection with the use of study drug, should be reported as AEs (serious or nonserious). This event should be identified as suicide or attempted suicide, and the method of the suicide or attempt should be provided. If an attempted suicide meets the criteria for an SAE, the event must be reported according to the guidelines in Section 6.3.5. Suicidal thoughts and preparation for suicide should also be regarded as AEs. All events of suicidality will be monitored via the C-SSRS.

Pregnancy in itself is not regarded as an AE unless there is a suspicion that the IP has interfered with the effectiveness of a contraceptive medication. (To be eligible for this study, WOCBP and at risk of pregnancy must be using a reliable method of contraception; see Inclusion Criterion #7, Section 4.1). Should a pregnancy occur, it must be reported in accordance with the procedures described in Section 13.3.

In the clinical study report (CSR), the terms used by the investigator to record AEs will be mapped to preferred terms using a standard AE dictionary, Medical Dictionary for Regulatory Activities (MedDRA).

Causality collection

The investigator will assess causal relationship between IP and each AE (ie, their relationship to study drug), and answer "yes" or "no" to the question, "*Do you consider that there is a reasonable possibility that the event may have been caused by the investigational product.*"

For SAEs, causal relationship will also be assessed for other medication and study procedures. Note that for SAEs that could be associated with any study procedure, the causal relationship is implied as “yes.”

A guide to the interpretation of the causality question is found in [Appendix B](#) to the CSP.

Adverse events based on signs and symptoms

All AEs spontaneously reported by the patient or reported in response to the open question from the study personnel: “*Have you had any health problems since the previous visit/you were last asked?*,” or revealed by observation will be collected and recorded in the eCRF. When collecting AEs, the recording of diagnoses is preferred (when possible) to recording a list of signs and symptoms. However, if a diagnosis is known and there are other signs or symptoms that are not generally part of the diagnosis, the diagnosis and each sign or symptom will be recorded separately.

Adverse events based on examinations and tests

The results from protocol-mandated laboratory tests and vital signs will be summarized in the CSR. Deterioration as compared to baseline in protocol-mandated laboratory values, and vital signs should therefore only be reported as AEs if they fulfill any of the AE criteria or are the reason for discontinuation of treatment with the IP, or at the discretion of the investigator.

If deterioration in a laboratory value/vital sign is associated with clinical signs and symptoms, the sign or symptom will be reported as an AE and the associated laboratory result/vital sign will be considered as additional information. Wherever possible, the reporting investigator uses the clinical, rather than the laboratory term (eg, anaemia versus low Hb value). In the absence of clinical signs or symptoms, clinically relevant deteriorations in non-mandated parameters should be reported as AE(s).

Deterioration of a laboratory value, which is unequivocally due to disease progression, should not be reported as an AE/SAE.

Any new or aggravated clinically relevant abnormal medical finding at a physical examination as compared with the baseline assessment will be reported as an AE.

Underlying disease progression

Disease progression can be considered as a worsening of a patient’s condition attributable to the disease for which the IP is being studied, which in this study refers to the condition of OIC. Adverse events which are due to disease (ie, OIC) progression, in the opinion of the investigator, should not be reported as an AE, unless they meet SAE criteria (eg, hospitalization, etc., see Section 6.3.3).

Of note, patients in this study must have an opioid-requiring pain condition in order to participate. Any day-to-day type fluctuations in pain control common in this population should not be reported as AEs, unless they meet SAE criteria (eg, hospitalization, etc., see Section 6.3.3).

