5.5.2 Doses and treatment regimens

5.5.2.1 NKTR-118

Patients randomized to the NKTR-118 treatment arm will receive NKTR-118 25 mg daily during the 52-week treatment period of the study (Days 1 to 365). They will be instructed to take 1 tablet daily 1 hour before eating in the morning.

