5.5.2.2 Usual Care

Patients randomized to the Usual Care treatment arm will follow a laxative treatment regimen for OIC determined by the investigator according to his/her best clinical judgment. For patients randomized to the Usual Care arm, the investigator is advised to treat the patient's OIC as he or she would usually do, following his/her clinical experience, and using laxative agents that are available for treatment of constipation or OIC in their respective country. The investigator may choose from a broad range of laxatives (see Section 5.6.2). However, peripheral μ -opioid antagonists, such as methylnaltrexone and naloxone containing products, are not allowed. The investigator may choose to re-start the laxative that the patient was taking prior to the start of the study if that agent was effective. The investigator will be free to modify the treatment regimen as he/she sees fit throughout the 52-week duration of the trial. No specific rescue laxative protocol is determined for patients randomized to receive Usual Care.

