13.2 Overdose

For the NKTR-118 program, overdose is defined as a dose ingested (or taken via any other route), confirmed by the patient (if possible), in excess of the total daily dose specified for the patient in their treatment group of the protocol. All reports of overdose (with or without associated AEs) are to be collected.

No cases of overdose have been previously reported with NKTR-118. No specific antidote for overdose with NKTR-118 has been identified to date.

██████████

If a patient on opioid therapy receives an overdose with NKTR-118, the patient should be monitored closely for evidence of opioid withdrawal symptoms and reversal of central analgesic effect. In cases of known or suspected overdose, symptomatic treatment as well as monitoring of vital functions should be performed. In cases of severe intoxication, intensive care procedures are recommended. Close medical supervision and monitoring should be continued until the patient recovers.

For recording purposes:

- If an overdose is reported during the course of a study, the patient is evaluated by the investigator/site staff to determine whether an SAE, non-serious AE, or no symptoms have been experienced after the overdose has been taken.
- If the patient experiences an overdose with an associated SAE, the investigator/site staff will capture details of the SAE and associated information on OVERDOSE, AELOG, and SAE modules in the eCRF.
- If the patient experiences an overdose with an associated non-serious AE, the investigator/site staff will capture details of the non-serious AE and associated information on OVERDOSE and AELOG modules in the eCRF.
- If the patient experiences an overdose with no symptoms, the investigator/site staff will capture details of the overdose and associated information on OVERDOSE module only in the eCRF.
- The OVERDOSE module (found in Module Package Library) is the preferred way of collecting overdose information. If the OVERDOSE module cannot be used, for example, if a CRO is managing the study and is unable to use the module, the Clinical Study Overdose template, may be used. This form is also used if the overdose occurred in a person not enrolled in the study, eg, accidental ingestion by a relative of the patient.

For reporting purposes:

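### Sections 6.3.4 and 13.2 disagree on whether a symptomless overdose is recorded as an adverse event, which can change AE incidence, mainly in the NKTR-118 arm

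*Protocol*

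**What the plan says.** Section 6.3.4 (Recording of adverse events) has two adjacent sentences on overdose. The first sends the reader elsewhere: "Should an overdose occur, it must be reported in accordance with the procedures described in Section 13.2". The second sets a rule of its own: "All overdoses, with or without associated symptoms, should be reported as AEs". The same section requires all AEs to be recorded on the eCRF.

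Section 13.2 (Overdose) treats an overdose and an AE as separate things: "All reports of overdose (with or without associated AEs) are to be collected". Its recording instructions have three branches. With an SAE, the site completes the OVERDOSE, AELOG and SAE modules. With a non-serious AE, the site is to "capture details of the non-serious AE and associated information on OVERDOSE and AELOG modules in the eCRF". With no symptoms, the site is to "capture details of the overdose and associated information on OVERDOSE module only in the eCRF".

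Section 13.2 defines overdose as a dose "in excess of the total daily dose specified for the patient in their treatment group of the protocol". For the active arm, Section 5.5.2.1 gives that dose: "Patients randomized to the NKTR-118 treatment arm will receive NKTR-118 25 mg daily during the 52-week treatment period of the study". For the comparator, Section 5.5.2.2 gives no dose and adds: "The investigator will be free to modify the treatment regimen as he/she sees fit throughout the 52-week duration of the trial".

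Section 12.2.1 tabulates all AEs in the clinical database and, separately, treatment-emergent AEs. A patient with an event counts once in the numerator, over all patients in the safety analysis set.

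**The concern.** The two sections give incompatible instructions for one event. A patient who once takes two NKTR-118 tablets and feels nothing has an AE record under 6.3.4 and none under 13.2.

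AE incidence is the first-listed safety variable (Section 6.3.1) in a trial whose primary objective is safety and tolerability, and the AE profiles of the two arms are compared descriptively (Sections 1.4 and 3.2). With about 130 centres, uneven recording would be hard to see in the tables and would need data queries to undo.

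The ambiguity is also unlikely to be balanced between arms. Only NKTR-118 has a protocol dose to exceed. NKTR-118 tablets are also dispensed and counted (Sections 5.7 and 5.7.1.1), whereas Usual Care patients obtain their own laxatives (Section 5.5.3) and no count of these is described.

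**Working it through.** **Text comparison.** The instructions for the three kinds of overdose are:

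| Event | Section 6.3.4 | Section 13.2 |
|---|---|---|
| Overdose with SAE | AE | OVERDOSE, AELOG and SAE modules |
| Overdose with non-serious AE | AE | OVERDOSE and AELOG modules |
| Overdose with no symptoms | AE | OVERDOSE module only |

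The first two rows agree. In the third, the word *only*, set against two branches that do name AELOG, excludes the AE log. Section 6.3.4 cannot be read as sponsor notification alone: it is the section on recording, and it requires AEs to be on the eCRF.

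**Inputs.**
- Planned N of about 1135 and 2:1 allocation (Section 3.1).
- Expected overdose rate: none given. Section 13.2 reports no earlier cases with NKTR-118.
- The protocol states no figure for this effect, so there is none to reproduce.

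**Arm sizes.** NKTR-118: 1135 x 2/3 = 756.7, about 757. Usual Care: 1135 x 1/3 = 378.3, about 378.

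**Effect per patient.** One NKTR-118 patient whose only event is a symptomless overdose moves any-AE incidence by 1/757 = 0.13 percentage points.

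**Illustrative range.** Let r be the share of NKTR-118 patients with a symptomless overdose and b the share with some other AE. Both are assumptions, treated as independent.
- Shift in incidence of the overdose term = r.
- Shift in any-AE incidence = r x (1 - b), since a patient with another AE is already in the numerator.

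| Assumed r | Patients (r x 757) | Overdose term, points | Any AE, b = 50%, points | Any AE, b = 80%, points |
|---|---|---|---|---|
| 0% | 0 | 0 | 0 | 0 |
| 0.5% | 3.8 | 0.5 | 0.25 | 0.1 |
| 1% | 7.6 | 1.0 | 0.5 | 0.2 |
| 2% | 15.1 | 2.0 | 1.0 | 0.4 |
| 5% | 37.8 | 5.0 | 2.5 | 1.0 |

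These are the differences between every site following 6.3.4 and every site following 13.2. Mixed practice falls in between. Under the 13.2 definition the Usual Care shift is 0.

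As a guide to b, Section 1.4 reports gastrointestinal AEs alone in 53% of the Phase II 25 mg group, in a study that Section 1.1 gives as 4 weeks long. Over a longer period b would probably be higher, which favours the right-hand columns.

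**The case against.** The strongest reply is that 6.3.4 already defers to 13.2. The cross-reference says *must*, the AE sentence says *should*, and only 13.2 gives module-by-module instructions. A site therefore has a procedure to follow, and wide variation between sites is possible but not shown. That softens the likely effect but does not remove the conflict. The AE sentence comes straight after the cross-reference, covers symptomless overdose expressly, and is contradicted by the procedure to which the reader has just been sent.

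Three stronger readings are tempting, and the documents do not support them.

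- *A reader might infer that AE incidence will in fact be shifted, by some tens of patients.* No overdose rate is given and none had been reported, so zero is a live value. The patient counts above are assumed event counts, not changes in any-AE incidence. They also suppose that the assumed rate applies to all 757 patients, while the protocol plans for about 125 with 12 months on NKTR-118. A 35-tablet bottle for a 30-day interval is a supply margin, not evidence of double dosing.
- *A reader might infer that Usual Care cannot produce such an event.* That holds only if the 13.2 definition is read into 6.3.4, which speaks of all overdoses. Both arms take opioids, and Section 12.1.1 counts Usual Care as study drug, so a site could log an opioid or laxative overdose in either arm.
- *A reader might infer that symptomless overdose should be kept out of the between-arm AE incidence.* That is an analysis preference that may belong in the SAP, which is not shown. It would also remove an event that 6.3.4 itself calls an AE. AEs are already tabulated by preferred term, so a logged overdose would be visible there.

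It is also fair to say that the between-arm comparison is secondary and descriptive.

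**Conclusion.** The contradiction is real: 6.3.4 calls for an AE record of a symptomless overdose and 13.2 restricts it to the OVERDOSE module. Sites may record the same event differently, and this can change AE incidence, mainly in the NKTR-118 arm. *Mainly* rests on applying the 13.2 definition, under which Usual Care has no protocol dose to exceed.

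The size is unknown and may be nil. The one firm figure is about 0.13 percentage points of NKTR-118 any-AE incidence per patient whose only event is a symptomless overdose, taking the planned 757 as the denominator. Incidence of the overdose term itself is affected directly. Since no statistical testing is planned, no error rate or power is touched. This is an internal inconsistency worth correcting because AE counting is the core of the trial, not because a large distortion has been shown.

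**What to change.** Amend 6.3.4 and 13.2 so that both give one recording rule for symptomless overdose, applied at all sites. State in the same place whether *overdose* in 6.3.4 carries the 13.2 definition or extends to opioids and laxatives in either arm. In the safety tables, show symptomless overdose on its own line by arm, so that its contribution to the AE counts can be seen whichever rule is chosen.

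The cost is about one sentence of protocol text and one table line. It is best done before data accrue, since records made under mixed rules would need site queries to harmonise.

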Adult patients who are receiving a stable maintenance opioid regimen (total daily dose of 30 to 1000 mg of oral morphine, or equianalgesic amount[s] of 1 or more other opioid therapies for a minimum of 4 weeks) for non-cancer-related pain and who report a history of <3 spontaneous bowel movements (SBMs)/week and at least 1 OIC associated symptom at screening and have a confirmed diagnosis of OIC will be eligible to be randomized.

Confirmed OIC is defined as:

- Documented <3 SBMs/week on average over the 2-week OIC confirmation period. Patients with uneven distribution of SBMs across the 2-week OIC confirmation period (0 SBMs in 1 week with ≥ 4 SBMs in the other week) will be excluded. In

addition to the SBM frequency criterion, patients must report ≥ 1 of the following symptoms in at least 25% of the bowel movements (BMs) recorded in the electronic diary (eDiary) during the OIC confirmation period: Bristol Stool Scale (BSS) stool type 1 or 2; moderate, severe or very severe straining, incomplete BM. Patients who have 0 BMs over the 2-week OIC confirmation period will not be randomized.

Investigational product, dosage and mode of administration

NKTR-118 25 mg tablets

Comparator, dosage and mode of administration

The study will include a Usual Care arm. For the Usual Care arm, investigators will be permitted to choose constipation treatment according to their best clinical judgment.

Duration of treatment

The study duration will be 54 to 58 weeks. The study will consist of 52 weeks of open-label treatment followed by a 2 week follow-up period. In addition, new patients will undergo an initial screening period lasting up to 2 weeks, and a 2-week OIC confirmation period, during which the diagnosis of OIC and stability of opioid regimen will be confirmed.

Outcome variable(s):

- **Safety**
 - Incidence, nature, and intensity of adverse events (AEs), treatment-related AEs, serious adverse events (SAEs), AEs leading to discontinuation, and specific safety areas of interest
 - Mean daily prescribed opioid dose
 - Mean bisacodyl dose per week (NKTR-118 group only)
 - Change from baseline in Numeric Rating Scale (NRS) pain score
 - Observed values and change from baseline in composite score of modified Himmelsbach scale
 - Changes in vital signs and physical examination
 - Changes in laboratory assessments (ie, chemistry, hematology, and urinalysis [U/A])
 - Changes in electrocardiograms (ECGs)
- **Health economics**

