12. STATISTICAL METHODS AND SAMPLE SIZE DETERMINATION BY ASTRAZENECA

12.1 Description of analysis sets

12.1.1 Safety analysis set

All randomized patients who received at least 1 dose of study drug (25 mg NKTR-118 or Usual Care) will be included in the safety analysis set. The safety analysis set will be used to assess safety and tolerability variables.

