12.2.1 Safety analyses

Adverse events will be coded using the MedDRA dictionary. Three sets of AE summaries will be generated: (1) all AEs recorded in the clinical database, (2) all TEAEs (as defined in Section 11.1.1), and (3) AEs occurring after the last dose of study drug.

Number of events and proportions will be tabulated by preferred term and system organ class. An event that occurred 1 or more times on the date of or subsequent to first dose of study drug will contribute 1 observation to the numerator of the proportion. The denominator of the proportion will comprise all patients in the Safety analysis set. Adverse events will also be

summarized by intensity and separately, by causality (as determined by the investigator). Should a patient experience the same preferred term/system organ class within multiple intensity or causality categories, the patient's worst occurrence (most severe/most related) will be retained in the tabulations. Serious AEs and commonly occurring AEs will be summarized in a generally similar manner. Adverse events of special interest may be further summarized and analysis of AEs occurring within specific time periods (e.g. after 3 months, after 6 months, etc.) may be considered.

Adverse events, SAEs, AEs leading to death, and AEs leading to study discontinuation will be tabulated for each treatment group. Descriptive statistics for time to onset and duration of select AEs may be summarized by treatment group. Adverse events that could potentially be indicative of centrally mediated opioid withdrawal, abuse potential, and bowel perforation will be identified prior to database lock and will also be summarized by each treatment group.

The mean daily opioid dose will be summarized for the following intervals: randomization to Month 1, Months 1 to 3, Months 3 to 6, Months 6 to 9, and Months 9 to 12. The mean bisacodyl dose per week will be summarized only for the NKTR-118 treatment group using descriptive statistics for the following intervals: randomization to Month 1, Months 1 to 3, Months 3 to 6, Months 6 to 9, and Months 9 to 12. The observed composite modified Himmelsbach score and change from baseline will be summarized by treatment group at Week 1, Months 1, 3, 6, 9, and 12 using descriptive statistics. The observed score and change from baseline in the NRS pain scores (average in the 7 days prior to the study visit) will be summarized by treatment group for Weeks 1 and 2, Months 1, 2, 3, 6, 9, and 12.

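### For non-serious AEs, causality and action taken are asked against the IP, with study drug used in two senses, so related AEs in the Usual Care arm cannot be interpreted beside those on NKTR-118

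*Protocol*

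**What the plan says.** Section 6.3.4 of the protocol governs how adverse events are recorded in both arms.

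- **Causality, all AEs.** The listed variable is "Investigator causality rating against the study drug (yes or no". The paragraph on causality collection then states: "The investigator will assess causal relationship between IP and each AE (ie, their relationship to study drug". The yes/no question put to the investigator names the investigational product as the possible cause.
- **Causality, SAEs only.** "For SAEs, causal relationship will also be assessed for other medication and study procedures".
- **Action taken.** The listed variable is "Action taken with regard to IP".

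The synopsis gives NKTR-118 25 mg tablets as the investigational product and Usual Care as the comparator. Section 5.5.1, on the identity of the IP, describes only NKTR-118.

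The outcome variables in the synopsis include "Incidence, nature, and intensity of adverse events (AEs), treatment-related AEs", and section 6.3.1 repeats this. Section 12.2.1 summarises AEs "by causality (as determined by the investigator". Section 12.2 says data are presented by the group randomized in this study. Section 2.2 makes a descriptive comparison with Usual Care the secondary objective.

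**The concern.** A patient on Usual Care may have cramps or diarrhea that the investigator attributes to the prescribed laxative. If the event is non-serious, no question names that laxative. Read literally, the causality answer is no, because the patient is not taking the IP. The same event on NKTR-118 can be rated related.

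The events concerned are common. Section 1.1 lists cramps, abdominal pain, nausea and diarrhea among the side effects of constipation treatments. Section 1.4 names abdominal pain, diarrhea and nausea as the most common side effects of NKTR-118. Attributable events of the same kind are thus expected in both arms, but the question is framed for one.

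The action-taken field has the same limit. In the Usual Care arm, "The investigator will be free to modify the treatment regimen as he/she sees fit throughout the 52-week duration of the trial". A laxative changed because of an AE has no place in a field that refers to the IP.

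At stake is a named safety variable in a study whose only between-arm comparison is descriptive. The SAP cannot recover an attribution that the eCRF did not collect.

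**Working it through.** **Step 1: what the causality question covers.**

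| Event | Causality to IP | Causality to other medication | Field that would capture a Usual Care laxative |
|---|---|---|---|
| Non-serious AE | Yes (6.3.4) | No | None, unless the site reads study drug to include it |
| SAE | Yes (6.3.4) | Yes (6.3.4) | Other medication, a separate variable |

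**Step 2: what study drug means.**

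- Section 6.3.4 equates the IP with study drug. The IP is NKTR-118, so Usual Care is excluded.
- Section 12.1.1 defines the safety set by receipt of "study drug (25 mg NKTR-118 or Usual Care" treatment, so Usual Care is included.
- Section 5.8 sets the early termination visit for patients who have had either study drug or a Usual Care laxative. Usual Care is an alternative to study drug and so is excluded. Section 3.1.2 uses the same construction.

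No section tells a site which sense applies when it rates a Usual Care event. Appendix B pulls towards the narrow sense: its first factor asks whether the patient actually received the suspect drug.

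**Step 3: size, as an illustration.** The protocol states no related-AE rate, power or effect size, so there is no figure to reproduce. The inputs are:

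- N = 1135, randomized 2:1 (section 3.1): 1135 × 2/3 ≈ 757 on NKTR-118 and 1135 × 1/3 ≈ 378 on Usual Care.
- p = true proportion of patients with a treatment-attributable AE, assumed equal in both arms and varied from 5% to 30%.
- c = share of attributable Usual Care events that sites rate as related. c = 0 is the literal IP reading, c = 1 is the section 12.1.1 reading applied everywhere, and c = 0.5 is a mix.

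Related count on NKTR-118 = 757 × p. Related count on Usual Care = 378 × p × c. Apparent gap = p − c × p = p × (1 − c).

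| p | NKTR-118 (of 757) | Usual Care (of 378), c = 0 / 0.5 / 1 | Apparent gap in points, c = 0 / 0.5 / 1 |
|---|---|---|---|
| 5% | 38 | 0 / 9 / 19 | 5 / 2.5 / 0 |
| 10% | 76 | 0 / 19 / 38 | 10 / 5 / 0 |
| 20% | 151 | 0 / 38 / 76 | 20 / 10 / 0 |
| 30% | 227 | 0 / 57 / 113 | 30 / 15 / 0 |

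With no true difference between arms, the apparent gap runs from zero to the whole NKTR-118 rate, depending only on c. The protocol does not fix c, and nothing in the collected data would reveal it.

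**The case against.** The strongest case on the other side has five parts.

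- **SAEs have a second causality question.** This stands. Causality to other medication can cover a Usual Care laxative, so the gap is confined to non-serious AEs. It is a separate variable, however, and section 12.2.1 does not say that it feeds the causality summary.
- **The Usual Care count need not be zero.** This stands. A reader might infer that it is zero by construction. That follows only if every site takes study drug to mean NKTR-118, and section 12.1.1 says otherwise. Rollover patients now on Usual Care who had NKTR-118 earlier could also be rated related. The count is near zero or site-dependent, which is still not interpretable.
- **No between-arm table of related AEs is spelled out.** This stands in part. The sentence in section 12.2.1 listing what is tabulated for each treatment group does not mention treatment-related AEs. But they are a named safety variable, a causality summary is planned, and section 12.2 presents data by randomized group, so a by-arm layout is the natural reading. How to label the Usual Care column can be left to the SAP; what the eCRF asks cannot.
- **Discontinuations are recorded in both arms.** This stands. A reader might infer that intolerance is counted in one arm only. Section 6.3.4 asks of every AE whether it caused discontinuation from the study, and section 12.2.1 tabulates this by group. Freedom to change laxatives is a feature of the comparator, and no analysis described in section 12 uses the action-taken field.
- **The Usual Care arm still serves its purpose.** This stands. Sections 1.4 and 3.2 give that purpose as a baseline AE rate, which all-causality summaries supply. The documents do not support saying that the purpose is defeated.

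**Conclusion.** The point holds for non-serious AEs. Causality and action taken are asked against NKTR-118, and study drug carries two incompatible meanings. A by-arm summary of treatment-related AEs would therefore mix a drug attribution in one arm with a near-zero or site-dependent count in the other. About 378 patients, one third of those planned, are in the affected arm.

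The size cannot be estimated from the protocol. If true rates are equal, the spurious gap lies between zero and the full NKTR-118 related rate; the 5% to 30% range used above is assumed. A reader might go further and scale the Phase II GI AE rates in section 1.4 (53% at 25 mg, 48% on the corresponding placebo) by an assumed 25% to 75% judged related. Against zero, that gives 0.25 × 53% ≈ 13 to 0.75 × 53% ≈ 40 points. The documents do not support that estimate. They give no related fraction, the Phase II study lasted 4 weeks, placebo is not a laxative regimen, and the zero depends on the literal reading at every site.

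The all-causality AE, SAE and study-discontinuation summaries are sound on this point, and no statistical test is planned.

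**What to change.** 1. Use one definition of study drug throughout the protocol, and bring sections 5.8, 6.3.4 and 12.1.1 into line with it.
2. In section 6.3.4 and on the AE eCRF, ask causality against the assigned constipation treatment in each arm: NKTR-118, or the Usual Care laxative or laxatives current at onset. Word the action-taken field the same way.
3. Add a short instruction for rating causality when a Usual Care patient takes several laxatives or has recently changed.
4. If the eCRF cannot be changed, present treatment-related AEs for NKTR-118 only and mark Usual Care *not applicable*, never 0%.

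A separate causality field for bisacodyl rescue in the NKTR-118 arm is optional.

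The cost of items 1 to 3 is a small eCRF edit, a consistency pass through the protocol and some added site effort, because regimens in the Usual Care arm can change. The fallback costs essentially nothing. None of this alters treatment, visits or sample size.
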